## **g) Withdrawal of Subjects**

Participation is voluntary and there is no penalty if an individual chooses not to join the research study; their services will not be affected. If an individual enrolls in the study and later chooses to withdraw from the study, they may do so at any time without any penalty to them. They can simply withdraw from the study by telling the research staff in person when they are at study sites, or by contacting research staff by telephone or email.

Participants will be withdrawn from the study if they appear to be under the influence of alcohol or illegal drugs or are hostile to research staff. In such cases, they will not be paid for their time.

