## **9) Resources Available to Conduct the Human Research**

We will recruit and collect data from 20 individuals enrolled in the CSC programs who will participate in the intervention. Given that this study's purpose is to collect preliminary data about the intervention's impact on decision-making needs, the sample size is based on pragmatics rather than power, consistent with recommendations for pilot studies. We used the current rate of enrollment at the CSC program and a conservative estimate of study enrollment of 40% to arrive at the projected N.

Research staff for this study include the research assistant, the decision coaches at each of the CSC programs, and PI. The research assistant will dedicate at least 20 hours per week to recruitment and data collection during the study period. The decision coaches are also expected to dedicate at least 10 hours per week delivering the intervention, documenting contacts with participants, and participating in supervision via videoconference with the PI. The PI will dedicate at least 10 hours per week overseeing and managing the implementation of the study, supervising project staff, analyzing data, and completing other project tasks as needed.

Research staff for this study have received extensive training, including completion of the CITI social and behavioral health human subjects training. During weekly staff meetings, the research team will discuss ongoing issues regarding the research to ensure procedures are followed and issues are addressed appropriately.

Research staff have private, furnished office spaces at Temple University with access to Internet jacks, telephones, lockable file cabinets, teleconference equipment, and standard office equipment and supplies to facilitate research-related activities.

The CSC programs are equipped with a large workspace for employees that includes Internet jacks, telephones, lockable file cabinets, and standard office equipment and supplies. They have conference areas with teleconference capability that will be available for recruitment as well as private rooms that will be available for intervention meetings, telephone calls, and research interviews with participants.

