### b) Inclusion and Exclusion Criteria

The research assistant will determine eligibility in person at the CSC programs or over the telephone/videoconference by using a screening questionnaire with study criteria questions. Screenings conducted at the CSC programs will be conducted in a private room. Screen failures will be notified that they are ineligible for the study, but that this will not have an impact on their ability to continue to access CSC services. All information/materials collected during screening will be stored in a locked office in a locked filing cabinet and within password-protected and encrypted electronic files.

*Inclusion criteria* are: 1) 18-30 years of age; 2) experiencing early psychosis, defined as psychosis lasting 18 months or less between the time when threshold symptom criteria were reached (as determined by the admitting CSC program assessor) and the date of CSC program enrollment; 3) able to speak/understand English; 4) able to provide informed consent as assessed by research staff; and 5) enrolled in the CSC program for any period of time.

*Exclusion criteria* are: having a legal guardian or diagnosis of dementia, delirium, or intellectual disability as determined by the admitting CSC program psychiatrist. No individuals from special populations will be included.

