## **12) Risks to Subjects**

During the research interviews and participation in the study intervention, topics may come up that are distressing or triggering, including diagnoses, symptoms, and negative treatment experiences. We will attempt to

minimize this risk by detailing what topics will be covered before participants begin the interview and intervention.

Participants may become fatigued or uncomfortable during research interviews. We will attempt to minimize these risks by allowing participants to schedule the remainder of the interview/assessment for another time, and by informing them that they may omit questions, or simply discontinue the interview/assessment, at any time.

In the event that a participant has been harmed by the research, we will facilitate prompt receipt of their psychiatric or medical care. However, participants will be responsible for the costs of such psychiatric or medical treatment, directly or through medical insurance and/or other forms of medical coverage. Temple University and research staff will not be responsible for the cost of this treatment. This has been made explicit on the informed consent forms.

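### The withdrawal rule ends study participation, not just the visit, for apparent intoxication or hostility, so outcome data are lost and selective attrition of unknown size is possible

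*Combined protocol and SAP*

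**What the plan says.** Protocol section 11(g), Withdrawal of Subjects, first allows participants to leave whenever they choose. It then adds a staff-initiated rule, under which they "will be withdrawn from the study if they appear to be under the influence of alcohol or illegal drugs or are hostile to research staff". The next sentence reads "In such cases, they will not be paid for their time". No severity, repetition, assessor or second attempt is specified.

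Four other places bear on it:

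- Section 9: "Research staff for this study include the research assistant, the decision coaches at each of the CSC programs, and PI". The coaches are therefore on the list of research staff.
- Section 11(b): the exclusions are "having a legal guardian or diagnosis of dementia, delirium, or intellectual disability as determined by the admitting CSC program psychiatrist". Substance use is not among them.
- Section 12: fatigue or discomfort during research interviews is handled by "allowing participants to schedule the remainder of the interview/assessment for another time". Intoxication and hostility are not mentioned there.
- Section 11(f) and the last paragraph of the SAP: pre-post change is tested with paired t-tests, in the SAP on a DCS subscale. Neither gives a missing-data rule or an analysis population.

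Section 11(e) makes retention a feasibility measure, tracked under CONSORT guidelines. The documents do not say how staff-initiated withdrawals count towards it, whether a post-intervention assessment is still sought from those withdrawn, or whether their existing data are kept.

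**The concern.** The entry criteria admit people who use substances, and the withdrawal rule can then remove them from the study for how they present at a contact. A state that may pass by the next day is treated as the end of participation, while fatigue in the same interview leads to a new appointment.

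Two results are exposed. The first is the primary quantitative comparison: a paired test needs both scores, so anyone removed before post-intervention drops out of it. The second is acceptability. Section 12 expects distressing topics, including bad experiences of treatment, to arise in interviews and in the intervention, so hostility could be a reaction to what is being tested. If the rule reaches coaching, people in open conflict with the coach would leave before anyone asks them about the coach or the intervention. That argument does not depend on any assumption about DCS change.

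**Working it through.** **No figure to reproduce.** The planned number is 20, and "the sample size is based on pragmatics rather than power, consistent with recommendations for pilot studies". The documents give no effect size, SD of change, dropout rate or expected number of removals. The rates and differences below are therefore assumptions, shown as ranges.

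**What is lost.** In Table 1 (Procedures), the DCS is taken at baseline, during the intervention and at post-intervention. The Intentional Peer Support Scale (the relationship with the coach), the Satisfaction with Decision Scale, the qualitative measure of needs and the acceptability measure are taken at post-intervention only. A participant withdrawn before then contributes no paired DCS change and nothing at all on those four.

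**Bias in mean change.** Let k of 20 be removed, let the retained have mean change m_R, and let the removed have had mean change m_W if followed. The completers' mean is m_R. The mean over all 20 is [(20 − k)·m_R + k·m_W]/20. The difference is

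bias = (k/20) × (m_R − m_W).

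**Precision.** In SDs of change, the 95% half-width of a paired mean is t(0.975, n − 1)/√n with n = 20 − k (two-sided 5% assumed). For n = 20 it is 2.093/4.472 = 0.47; for n = 18, 2.110/4.243 = 0.50; for n = 16, 2.131/4 = 0.53. No other losses are included.

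| Removed k | Pairs | Half-width (SD) | Bias if equal change | Bias if 0.5 SD less | Bias if 1.0 SD less |
|---|---|---|---|---|---|
| 0 | 20 | 0.47 | 0 | 0 | 0 |
| 1 | 19 | 0.48 | 0 | 0.025 | 0.05 |
| 2 | 18 | 0.50 | 0 | 0.05 | 0.10 |
| 4 | 16 | 0.53 | 0 | 0.10 | 0.20 |

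**Retention.** With k removals and no other losses, retention is (20 − k)/20 if they count as losses: 95% for k = 1 (exact 95% interval 75 to 100%), 90% for k = 2 (68 to 99%) and 80% for k = 4 (56 to 94%). If they are dropped from the denominator, it is 100% in every case. The plan does not choose between these.

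**How many removals are conceivable.** Section 11(d) gives two interviews, one repeat DCS and weekly or biweekly meetings for about 1 to 3 months. That is roughly 2 + 1 + 2 = 5 to 2 + 1 + 13 = 16 contacts. If each contact carries an independent chance p of triggering the rule, expected removals are 20 × [1 − (1 − p)^m] for m contacts:

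- p = 1%: 1.0 for m = 5, 3.0 for m = 16.
- p = 2%: 1.9 for m = 5, 5.5 for m = 16.
- If only the three research contacts count (m = 3): 20 × (1 − 0.99³) = 0.6 at 1%, and 20 × (1 − 0.98³) = 1.2 at 2%.

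The values of p are illustrative; the documents offer none.

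**The case against.** A conduct rule need not mirror the entry criteria, and answers given while intoxicated are of doubtful value. Both points stand: stopping the assessment is reasonable. They do not explain why the participant must also leave the study.

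The no-payment sentence is the best textual defence. Section 16 pays only for the baseline and post-intervention assessments, so the rule may have been written with those interviews in mind. This makes its reach into coaching ambiguous, even though section 9 lists coaches as research staff. A reader might infer that one difficult coaching meeting certainly ends participation; the documents do not settle that. If a visit-level rule was intended, the present wording says something else and needs correcting.

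A reader might also infer that the results will be biased because the rule removes the people hardest to engage. Nothing in the documents shows this. The Background gives rates of service disengagement, not of intoxication or hostility, and does not link either to change on the DCS.

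It is tempting to put a percentage on the effect. If 2 to 4 people with zero change are removed and the rest improve by 0.5 SD, the true means are (18 × 0.5)/20 = 0.45 and (16 × 0.5)/20 = 0.40, so a reported 0.50 looks 11 to 25% too high. That rests wholly on assumed inputs. In absolute terms it is the 0.05 to 0.10 SD already in the table, well inside the confidence interval of a pilot.

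Finally, it would be wrong to say that these withdrawals could not be told apart from participants' own decisions to leave. CONSORT tracking could record the reason; the plan simply does not require the split.

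**Conclusion.** The point holds as a risk created by the wording. Followed as written, section 11(g) gives up post-intervention data that rescheduling could keep, and the planned paired tests and acceptability summaries then rest on completers. The possible DCS bias runs from zero (equal change) to about 0.05 SD for 2 removals or 0.10 SD for 4 (0.5 SD less change in those removed), doubling if the difference is 1.0 SD. With 1 or 2 removals that is small beside a half-width of about 0.5 SD. The loss of acceptability and coach-relationship data from those removed cannot be expressed in these units, but in a study meant to refine the intervention it may matter more. The effect on reported retention is undefined until the denominator is fixed. Neither the number of removals nor the direction of any selection can be known from the documents. This is a cheap improvement to make, not a flaw that undermines the pilot.

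**What to change.** 1. In section 11(g), provide that when a participant appears intoxicated at a research assessment, that assessment is stopped and rescheduled. Extend the section 12 rescheduling provision to cover this, since it now applies only to fatigue or discomfort.
2. Separate ending a visit, or ending coaching, from withdrawal from the study. Still seek the post-intervention assessment unless the participant withdraws consent or the study team judges contact unsafe. Section 8 provides remote research interviews only when COVID-19 prevents meeting in person, so any remote fallback would have to be written in.
3. In the SAP, report staff-initiated withdrawals with reasons, apart from participant-initiated ones. Keep them in the retention denominator, and keep data already collected.
4. The study team should state whether the hostility rule covers coaching meetings and when hostility ends participation. That involves staff safety and is theirs to decide, as is whether coaching continues.

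The cost is an IRB amendment of about a paragraph, a few reporting lines in the SAP, some rescheduled visits, and a retention figure that may be slightly less favourable.

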## **12) Risks to Subjects**

During the research interviews and participation in the study intervention, topics may come up that are distressing or triggering, including diagnoses, symptoms, and negative treatment experiences. We will attempt to

minimize this risk by detailing what topics will be covered before participants begin the interview and intervention.

Participants may become fatigued or uncomfortable during research interviews. We will attempt to minimize these risks by allowing participants to schedule the remainder of the interview/assessment for another time, and by informing them that they may omit questions, or simply discontinue the interview/assessment, at any time.

In the event that a participant has been harmed by the research, we will facilitate prompt receipt of their psychiatric or medical care. However, participants will be responsible for the costs of such psychiatric or medical treatment, directly or through medical insurance and/or other forms of medical coverage. Temple University and research staff will not be responsible for the cost of this treatment. This has been made explicit on the informed consent forms.

### **13) Potential Benefits to Subjects**

There is no direct benefit from taking part in the research other than expanding knowledge that may inform policies and practices at the societal level.

### **14) Privacy and Confidentiality**

PHI collected during the study is limited to participant's self-reported contact information (e.g., name, address) and psychiatric diagnosis. PHI will not be disclosed, except as may be required by law. Any information about child abuse or intent to harm self or others will be reported to authorities, as required by law. Research staff will be the only people with access to this data, with the exception of authorized representatives of the Temple University or Philadelphia Institutional Review Board (IRB), the National Institute of Mental Health (the study sponsor), and the Office of Human Research Protections (OHRP).

Completed interviews will contain a coded identification number to prevent loss of confidentiality, and any identifying information will be removed from interview transcripts. Confidentiality of data files will be achieved by separating code numbers from individual identifying information. Information taken about participants will only be kept electronically in encrypted, password protected files and hard copies will be stored in locked cabinets in a locked office. Data sources containing identifiers (i.e., regulatory documents such as the eligibility screener and contact information form, clinical characteristic form) will always be kept separate from other research data in encrypted, password-protected files. Participant files will only be made available to personnel involved in the study through the use of access privileges and passwords. All published reports will contain data reported either in aggregate form (where no individual responses

can be identified), or in composite individual examples that are constructed so that identification is impossible. Individual examples or quotations that may be presented in published reports will use pseudonyms, so that participants' identity will be protected. Audio recordings will be secure and confidential per the transcription service provider's non-disclosure agreement and encryption software. Audio-recordings will be immediately deleted from the recorder after successful uploading to the transcription provider's secure site. All other data collected from this study will be kept for 7 years after the last publication.

In accordance with study sponsor guidelines, this study will be registered and de-identified results information (including participant flow, demographic and baseline characteristics, outcomes and statistical analyses, adverse events, the protocol and statistical analysis plan, and administrative information) will be submitted to ClinicalTrials.gov.

## **15) Economic Burden to Subjects**

There are no costs to participants associated with participation in this research study.

## **16) Subject Compensation**

Participants will receive \$20 for completing the baseline assessment and an additional \$30 for completing the post-intervention assessment. Participants will be paid via electronic gift cards. Upon each payment, they will sign a receipt form to document that they were paid.

## **17) Consent Process**

A particular issue related to our studies is that the research literature has long suggested that persons diagnosed with schizophrenia have cognitive impairments and that this is associated with impaired ability to make informed consent decisions. This has led some to conclude that people with psychiatric impairments cannot provide informed consent and therefore should not participate in research. Peer advocates have criticized this perspective as taking away their rights to participate in research. Carpenter et al. (2000) also found evidence, however, that more exhaustive consent procedures could enhance ability to consent. This educational remediation approach included multiple sessions where information was provided multiple times, questions were asked, and potential participants were prompted to help them fully understand the protocol. Our consent procedures will utilize these methods in addition to the INVESTIGATOR GUIDANCE: Informed Consent (HRP-802).

Our process for ensuring that all study participants provide fully informed consent will involve the following steps -- The first line of screening will be through contact between the research assistant or PI and the potential

participants. The research assistant or PI will meet with potential participants in a private room at Temple University or at the CSC programs, or via telephone or videoconference. The research assistant or PI provides a brief overview of the study and makes an initial assessment of their ability to understand and recall the following issues: what participants are asked to do, the voluntary nature of the study, data collection procedures, and nature of confidentiality. An interview is scheduled with those who are able to recall the information provided and demonstrate an understanding of all areas. Those who have problems with the initial assessment are asked if they can be contacted at a later time to discuss the project. A second assessment is conducted with the research assistant or PI. This assessment will assess recall from the previous conversation. Perfect recall is not expected. Poorly recalled information will be targeted during the review of the informed consent form and study procedures. The research assistant or PI will spend up to an hour with potential participants reviewing the consent forms. All forms are read aloud with the potential participant and they are again asked to recall information about the study. Prompts are given to facilitate recall. If the potential participant is able to recall pertinent information about the study without prompts, they are viewed as being able to give informed consent and will proceed with signing the consent form. If the research assistant or PI obtains informed consent from participants via telephone/videoconference, the participant will electronically sign the consent form in RedCap. All consent forms will be maintained in the case file along with all identifying information in a locked cabinet that is kept in a secure office.

## **18) Sharing of Results or Incidental Findings with Subjects**

After qualitative interview transcription, participants will be offered the opportunity to review their interview transcripts in order to ensure that meaning and ideas are accurately represented. Transcript copies will be emailed to participants via TUSafesend (a Temple University resource that provides a secure method for transferring files containing confidential information) or mailed to participants in opaque envelopes marked “confidential” (depending on the participant’s preference). On a separate page, participants will be asked to provide written feedback regarding whether the transcripts match their experience, and will be invited to make changes or additions to their statements. Participants will be provided with instructions for how to return comments via TUSafesend. Pre-paid return postage for mailed transcripts will be provided for participants to return comments to the researchers if they so choose. The contact information of the research assistant will also be provided in case participants have questions or prefer to offer their feedback verbally. We will allow two weeks for participants to return feedback before proceeding with further analysis. Participants will not receive additional compensation for providing this feedback.

## **Statistical Analysis Plan**

Demographic and clinical variables will be summarized with means and standard deviations. Dichotomous variables will be summarized with frequencies and percentages. Parameter estimates will be bound by 95% confidence intervals. Analyses will be conducted using SPSS Version 24. Feasibility data will also be reported using descriptive statistics.

*Mixed Methods Analysis.* Quantitative acceptability data will be reported using descriptive statistics. Per qualitative analysis recommendations, open-ended acceptability questions will be audio-recorded and professionally transcribed verbatim. The research assistant will proofread transcripts, making notes regarding participants' experiences with the intervention in each interview. The research assistant and PI will then use notes to create an initial draft of coding categories. Then, using the Constant Comparison Method, the research assistant and PI will independently code each transcript and discuss differences in coding to consensus, which could involve creating new codes or collapsing existing ones. After refining the code list, the final coding of each interview will be double-checked for accuracy. Data analysis will be facilitated using NVivo software. Member checking will be accomplished by inviting participants to review and provide feedback on their interview transcripts and on the codes developed. Initial analysis from the first three interviews will be conducted to inform subsequent data collection. As open-ended questions do not parallel survey questions, acceptability data will be interpreted and reported contiguously. Findings will inform intervention refinement for the R01.

To examine within-group differences in quantitative decision-making targets pre- and post-intervention, we will conduct a paired samples t-test using DCS Factors Contributing to Uncertainty subscale scores. Responses to open-ended questions about decision-making targets will be analyzed qualitatively using the same procedure described previously. The parallel structure of the qualitative interview to the DCS will enable quantitative and qualitative data to be merged and reported through narrative weaving. Integration of these data will provide a more nuanced understanding of whether and how the intervention engages decision-making targets than use of either type of data alone, and will be most informative for intervention refinement. Should quantitative and qualitative analyses yield discrepant findings, we will assess reasons for conflicting results (e.g., low power, question structure/content) and revise procedures accordingly for the R01 study.
